
To evaluate the effect of AMG 301 compared to placebo on the change from the baseline period in monthly physical impairment domain score as measured by the Migraine Physical Function Impact Diary (MPFID)	
Change from the baseline period in physical impairment domain scores as measured by the MPFID over the last 4 weeks of the 12-week double-blind treatment period

Objectives	Endpoints

To evaluate the effect of AMG 301 compared to placebo on the change from the baseline period in monthly impact on everyday activities domain score as measured by the MPFID	
Change from the baseline period in impact on everyday activities domain scores as measured by the MPFID over the last 4 weeks of the 12-week double-blind treatment period.

To evaluate the safety and tolerability of AMG 301	
Incidence of treatment-emergent adverse eventsChange from baseline in clinical laboratory values and vital signs

The secondary estimands for each of the secondary objectives except the last one are similar to the primary estimand but differ in the following ways:

- The variables are the endpoints listed above for each secondary objective
- The population-level summary measure for the first secondary objective is the difference in proportions of subjects who achieve at least a 50% reduction in monthly migraine days between each AMG 301 group and the placebo group

The estimands for the last secondary objective is similar to the primary estimand but differ in the following ways:

[figure not shown]
- The variables are the incidence of adverse events and change from baseline in clinical laboratory values and vital signs during the 12-week double-blind treatment period
- The population-level summary measures for the incidence of adverse events is the count of adverse events during the 12-week double-blind treatment period and the difference in means for the change from baseline variables for each AMG 301 treatment group and the placebo group
- The intercurrent event, adherence to treatment will be ignored and the secondary endpoint will be assessed for all subjects in the target population**

CCI

CCI

CCI

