9.1 General Considerations

The primary objective of this study is to evaluate the effect of AMG 301 compared to placebo on the change from the baseline period in monthly migraine days, in subjects with CM or EM.

The primary analysis will be performed when the last randomized subject completes the week 12 assessment or is discontinued from the study and all data are collected for the primary endpoint. The final analysis for the study including DBTP and safety follow-up phase will be performed at the end of the study.

Subjects will be analyzed based on their randomized treatment group assignment.

Summary statistics by each treatment group will be tabulated at each visit. For continuous endpoints, the descriptive statistics include: number of observations, means, medians, standard deviations, standard errors, first and third quartiles, minimums and maximums, and 2-sided 95% confidence intervals of the means (confidence intervals will be provided for efficacy endpoints only). For categorical endpoints, the summaries will contain the number and percentage of subjects in each category.

[figure not shown]
Change from baseline for efficacy endpoints during the DBTP will be summarized using the study baseline.

Primary analyses for efficacy endpoints are based on a linear mixed effects model including treatment group, baseline value, stratification factors, scheduled visit, and the interaction of treatment group with scheduled visit in the model.

Unadjusted p-values (not adjusted for multiple comparisons) will be provided for the comparisons between each AMG 301 treatment group vs. the placebo group for efficacy endpoints. For continuous efficacy endpoints, the adjusted mean change from baseline for each treatment group, and the adjusted treatment difference compared to placebo, associated 95% confidence intervals, and p-values for pairwise comparisons will be reported. For dichotomous efficacy endpoints, adjusted odds ratios compared to placebo, associated 95% confidence intervals, and p-values will be reported. Values for stratification factors as used during randomization will be utilized in the efficacy analysis instead of the subject's actual value. However, the actual value will be used in analyses of baseline characteristics or in the subgroup analyses of the efficacy endpoints.

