9.5 Efficacy Analyses

Endpoint	Statistical Analysis Methods
Primary	
The primary endpoint, change in monthly migraine days from the baseline period to the last 4 weeks of the 12-week DBTP, will be analyzed using the generalized linear mixed effects model including treatment group, baseline value, stratification factors, scheduled visit, and the interaction of treatment group with scheduled visit using the PAS without any subject-level imputation for missing data. The primary endpoint will be tested for each AMG 301 treatment group (AMG 301 420 mg SC injections Q2W and AMG 301 210 mg SC injections Q4W) compared to the placebo group using appropriate contrasts for pairwise comparisons. Each AMG 301 dose will be compared to placebo at an alpha of 0.05 to maintain the family-wise type I error at 0.10. The mean change from the baseline period for each treatment group, and the treatment difference, 95% confidence intervals, and p-values will be reported.
 
Sensitivity analyses for the primary endpoint include an analysis of covariance model using data through week 12, in which missing values will be imputed using multiple imputation assuming MNAR up to week 12.

Secondary	
• At least a 50% reduction from the baseline period in monthly migraine days in the last 4 weeks of the 12-week double-blind treatment period: Comparison between treatment groups will be performed using CMH tests on observed data with stratification factors. The odds ratio for each AMG 301 treatment group versus placebo group, associated 95% confidence intervals, and unadjusted p-values will be reported. Sensitivity analyses for response include: a logistic regression model using data from week 9 through week 12, adjusting for baseline values where missing values will be imputed as non-responders.
• Change from the baseline period in monthly acute migraine-specific medication days in the last 4 weeks of the 12-week double-blind treatment period: The same analysis methods will be used as for the primary endpoint. Refer to Table 5 for details on other secondary endpoints.
CCI	

The primary analysis of efficacy endpoints will utilize the PAS. Subjects will be analyzed according to their randomized treatment group regardless of the actual treatment received during the study.

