For primary analysis at week 12, the continuous change from baseline efficacy endpoints calculated by the method as specified in [Section 5.6](#) will be analyzed using generalized linear mixed effect models including treatment group, stratification factors, scheduled visit, the interaction between treatment group and scheduled visit and the baseline value on observed data. The dichotomous efficacy endpoints will be analyzed using the stratified Cochran-Mantel-Haenszel (CMH) test after the missing data are imputed as non-response. Detailed primary analysis methods, sensitivity analyses, and covariates included in the models are summarized in the table below.

Table 9-1. Summary of Efficacy Endpoints and Analysis Methods

Endpoint	Primary Summary and Analysis Method	Sensitivity Analysis
Primary Endpoint		
Change in monthly migraine days from baseline to the last 4 weeks of the 12-week DBTP (Note: Results from time points other than week 12 during the DBTP will also be generated in the same generalized linear mixed effect model.)	Analysis Method I: 1. Summary statistics by visit using observed data 2. Least squares means from a generalized linear mixed effect model including treatment group, baseline values, stratification variables, scheduled visit, and interaction of treatment and scheduled visit using observed data	1. Summary statistics by visit and analyze using an ANCOVA model with multiple imputation assuming MNAR(control-based pattern imputation) 2. Summary statistics by visit and analyze using an ANCOVA model with observed data 3. Subgroup analyses: Same as primary summary and analysis method.

Page 1 of 3

Footnotes defined on last page of the table

Table 9-1. Summary of Efficacy Endpoints and Analysis Methods

Endpoint	Primary Summary and Analysis Method	Sensitivity Analysis
Secondary Endpoints		

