At least a 50% reduction from baseline in monthly migraine days in the last 4 weeks of the 12-week DBTP (Note: Results from time points during DBTP will also be generated in the same model.)	1. Summary statistics by visit using observed data 2. Stratified Cochran-Mantel-Haenszel (CMH) Test	1. Summary statistics by visit and analyze using a logistic regression model, and using responder rate calculated using monthly migraine days 2. A stratified Cochran-Mantel-Haenszel (CMH) test will be used after the missing data are imputed as non-response 3. A generalized linear mixed effects model will be used on observed data 4. Subgroup analyses: Same as primary summary and analysis method.
Change from baseline in monthly acute migraine-specific medication treatment days in the last 4 weeks of the DBTP (Note: Results from individual time point during the DBTP will also be generated in the same generalized linear mixed effect model.)	Analysis Method I (see above)	Analysis Method II: 1. Summary statistics by visit and analyze using an ANCOVA model with multiple imputation, assuming MNAR
Change from baseline in monthly physical impairment scores as measured by MPFID at assessment time points (Note: Results from individual time point during the DBTP will also be generated in the same generalized linear mixed effect model.)	Analysis Method I	N/A

Footnotes defined on last page of the table

Page 2 of 3

Table 9-1. Summary of Efficacy Endpoints and Analysis Methods

Endpoint	Primary Summary and Analysis Method	Sensitivity Analysis
Change from baseline in monthly impact on everyday activities scores as measured by MPFID at assessment time points (Note: Results from individual time point during the DBTP will also be generated in the same generalized linear mixed effect model.)	Analysis Method I	N/A
CCI	Analysis Method I	N/A
	
• Summary statistics by visit using observed data• Stratified CMH test	N/A

Page 3 of 3

^a The same analyses methods will be applied to the endpoints:

Change from baseline in headache impact scores as measured by HIT-6
Change from baseline in monthly average severity of migraine pain
Change from baseline in monthly acute headache medication treatment days.
Change from baseline in migraine-related disability and productivity as measured by MMIDAS
Change from baseline in monthly days with physical impairment as measured by the MPFID

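### The 50% responder estimand is a difference in proportions but the readable analysis plans only an odds ratio; the CMH data set is contradictory, and the adverse-event estimand does not match the planned tables

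*SAP*

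**What the plan says.** **Responders.** For the 50% responder objective, SAP 2.1 states: "The population-level summary measure for the first secondary objective is the difference in proportions of subjects who achieve at least a 50% reduction". SAP 9.1 then plans: "For dichotomous efficacy endpoints, adjusted odds ratios compared to placebo, associated 95% confidence intervals, and p-values will be reported". The secondary-endpoint entry in SAP 9.5 repeats this: "The odds ratio for each AMG 301 treatment group versus placebo group, associated 95% confidence intervals, and unadjusted p-values will be reported". SAP 9.5.2 and protocol 10.4.3.2 also name an odds ratio for the full-set comparison.

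**Data for the CMH test.** The same entry in SAP 9.5 says: "Comparison between treatment groups will be performed using CMH tests on observed data with stratification factors". SAP Section 10, which records deliberate departures from the protocol, agrees. SAP 8.3 places non-responder imputation under sensitivity analyses, and the sensitivity column of Table 9-1 reads: "A stratified Cochran-Mantel-Haenszel (CMH) test will be used after the missing data are imputed as non-response". The paragraph directly above Table 9-1 describes the week 12 primary analysis differently: "The dichotomous efficacy endpoints will be analyzed using the stratified Cochran-Mantel-Haenszel (CMH) test after the missing data are imputed as non-response".

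**Adverse events.** In SAP 2.1 the endpoint and the variable are incidence, but the summary measure "is the count of adverse events during the 12-week double-blind treatment period". SAP 5.1.2 defines treatment-emergent events up to 126 days after the end of investigational product. SAP 5.6 counts a subject once per event. SAP 9.6.2 tabulates subject incidence, and SAP 7.3 combines the double-blind and follow-up phases at the final analysis.

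**Laboratory values and vital signs.** The same bullet of SAP 2.1 continues: "and the difference in means for the change from baseline variables for each AMG 301 treatment group and the placebo group". SAP 9.6.3 and 9.6.4 plan change-from-baseline summaries together with shift and threshold tables.

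**The concern.** An estimand fixes the quantity to be estimated, and the analysis section should then say how. For responders the declared quantity is an absolute difference, while the planned one is a ratio of odds. One does not determine the other without the placebo rate, so an odds ratio alone does not report the declared effect.

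The conflict over observed and imputed data is a separate matter. It would exist even if SAP 2.1 named an odds ratio. It changes what enters the main CMH test, and hence the p-value and any effect estimate.

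For adverse events the declared measure and the planned one differ both in kind (events against subjects) and in time window. A reader looking for the 12-week result that SAP 2.1 promises would find no table explicitly planned for it.

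**Working it through.** **1. Odds ratio against difference.** The documents give no response rates, so placebo rates are assumed. With placebo proportion p0 and odds ratio OR, odds1 = OR × p0/(1 − p0), p1 = odds1/(1 + odds1), and the difference is p1 − p0.

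| OR | p0 = 15% | p0 = 40% |
|---|---|---|
| 1.5 | 20.9% − 15% = 5.9 points | 50.0% − 40% = 10.0 points |
| 2.0 | 26.1% − 15% = 11.1 points | 57.1% − 40% = 17.1 points |

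The same odds ratio therefore corresponds to clearly different values of the declared estimand.

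**2. Interval for the difference.** Allocation 4:3:3 of 335 gives 134 on placebo and 100.5 per dose (100 used). With assumed response of 30% and 40% and no missing data, the crude 95% half-width is 1.96 × √(0.30 × 0.70/134 + 0.40 × 0.60/100) = 12.3 points. Stratifying by CM/EM alone (67 and 50 per stratum, equal weights, +10 points in each stratum) gives 12.1 points for placebo rates of 20%/40% and 11.2 points for 10%/50%. Stratifying thus narrows the half-width by 12.3 − 12.1 ≈ 0.3 (before rounding) to 12.3 − 11.2 = 1.1 points. Region, the other stratification factor, is left out of this sketch.

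**3. Observed data against non-responder imputation.** With missing fractions m1 (dose) and m0 (placebo), and 40% and 30% among those observed, the imputed difference is 0.40(1 − m1) − 0.30(1 − m0). The observed difference is 10.0 points throughout. SAP 8.3.3 uses more than 20% as its own example of high missingness; all fractions below are assumed.

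| m1 | m0 | Imputed difference |
|---|---|---|
| 5% | 5% | 38.0 − 28.5 = 9.5 |
| 10% | 10% | 36.0 − 27.0 = 9.0 |
| 20% | 20% | 32.0 − 24.0 = 8.0 |
| 15% | 5% | 34.0 − 28.5 = 5.5 |
| 5% | 15% | 38.0 − 25.5 = 12.5 |

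Over placebo/dose rates from 20%/30% to 40%/50%, the last two rows run from 6.5 to 4.5 and from 11.5 to 13.5. These figures measure the data-set conflict in 9.5, not the mismatch between difference and odds ratio.

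**4. Adverse-event window.** The plan's own figure reproduces: 18 weeks × 7 = 126 days. The week 10 dose has target day 71, so the window ends on day 71 + 126 = 197. That is (197 − 1)/7 = 28 weeks against 12, a ratio of 28/12 = 2.3. Weeks 13 to 28 make up 16/28 = 57% of it. Even a subject dosed only on day 1 has a window to day 1 + 126 = 127, which is 43 days past day 84, provided the subject stays in the study.

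**5. Count against incidence.** As an assumed illustration, 40 of 100 subjects affected is 40% incidence whether each has one event or three, but the count is 40 × 1 = 40 or 40 × 3 = 120.

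**The case against.** **The odds ratio is a fixed choice.** The protocol and three SAP sections agree on it with an interval, so one could simply reword SAP 2.1. That would remove the inconsistency. But the declared between-group effect is an absolute difference, and adding its estimate costs almost nothing. By-arm percentages are tabulated (SAP 9.1), so a crude difference can be worked out by hand; what is missing is a stated estimator, interval and data set.

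**Redaction.** Appendix B and parts of 9.1 and 9.5 are blacked out, and a risk-difference option may be there. The point is therefore limited to the readable text. Redacted code would not remove the contradiction within 9.5. SAP 9.5.2 does mention a treatment difference or odds ratio, but for subgroup analyses, most naturally as a difference for continuous endpoints and an odds ratio for binary ones.

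**One stray sentence.** The secondary entry in 9.5, Section 10, 8.3 and Table 9-1 all favour observed data as the main analysis. This stands. A reader might infer that the sponsor is free to choose after unblinding; the weight of the text does not support that. It supports a contradiction that needs correcting.

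**Loose adverse-event wording.** *Count* may mean the numerator of an incidence table. SAP 5.6 defines incidence per period, SAP 7.2 says follow-up data are also summarized, and Table 9-3 mentions a period of interest. These narrow the gap and may imply a double-blind summary, but none explicitly names a table restricted to that period.

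**Laboratory values and vital signs.** A reader might infer that a between-group difference is promised and missing. The responder bullet says *between* groups, whereas this one says *for each* group, and it can be read as mean change by arm, which 9.6.4 provides for vital signs. SAP 9.6.1 rules out between-group safety testing. Only clarification is warranted here.

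**Conclusion.** The point holds in three parts: the responder summary measure in SAP 2.1 has no matching estimator or interval in the readable analysis text; SAP 9.5 contradicts itself on the data for the main CMH test; and the adverse-event measure in 2.1 differs in kind and window from the planned tables.

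Severity is minor. Only secondary endpoints are affected, and the primary, medication-day and MPFID estimands match their planned least-squares mean differences. The data-set conflict has the largest numerical effect: on assumed rates, a 10-point difference becomes 8.0 with 20% missing in both arms, or 5.5 to 12.5 with unequal 15%/5% missingness. The choice between a crude and a stratified interval is small, at 0.3 to 1.1 points of half-width. The adverse-event window is 28 weeks against 12 for a subject dosed through week 10.

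A reader might infer that no hypothesis test is touched. That is not so: settling the data set fixes the input and the p-value of a secondary test. All response and missingness rates are assumptions.

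**What to change.** (a) Before unblinding, correct the paragraph above Table 9-1 so that it agrees with the secondary entry in 9.5, Table 9-1 and Section 10 (observed data as main analysis, non-responder imputation as sensitivity), or state the reverse consistently in all of those places and in 8.3. Acknowledge that this fixes the input and p-value of a secondary test.

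(b) In SAP 9.5, 9.5.2 and Table 9-1, add the Mantel-Haenszel stratum-weighted difference in response proportions for each dose against placebo, with a 95% confidence interval, using the randomization strata and the same data as the main CMH test. Keep the odds ratio beside it.

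(c) In SAP 9.6.2, add a subject-incidence table of treatment-emergent events restricted to onset in the double-blind period. In 2.1, replace the count with subject incidence.

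(d) In 2.1, state that the measure for laboratory values and vital signs is mean change by arm.

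Cost: SAP wording, one extra estimate and one extra table. No new data are needed and the primary test is unchanged.

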2.2 Hypotheses and/or Estimations

In subjects with migraine, AMG 301 provides a greater reduction from the baseline period in monthly migraine days, compared to placebo.

The primary endpoints of the study will be tested for each of the AMG 301 210 mg and AMG 301 420 mg groups compared to placebo, respectively, at significance levels of 0.05 and 0.05, respectively, to maintain a familywise type I error of 0.10.

- Null Hypothesis: In subjects with migraine, the AMG 301 treatment group is not different from placebo, in terms of the reduction of the monthly migraine days from baseline.
- Alternative Hypothesis: In subjects with migraine, the AMG 301 treatment group is different from placebo, in terms of the reduction of the monthly migraine days from baseline.

3. Study Overview

3.1 Study Design

This is a phase 2a, multicenter, randomized, double-blind, placebo-controlled, 3-arm parallel-group study of subjects with chronic migraine (CM) or episodic migraine (EM). Approximately 335 subjects will be randomized 4:3:3 to placebo, AMG 301 210 mg via SC injections QM, or AMG 301 420 mg via SC injections Q2W, respectively. The randomization will have 2 stratification factors: baseline migraine frequency (CM versus EM) and region (North America versus Rest of World).

Interactive Voice Response (IVR)/Interactive Web Response (IWR) system will be used to facilitate randomization and stratification and investigational product assignment.

Stratification at Randomization:

Baseline migraine frequency (CM versus EM; limit both CM and EM randomization to approximately 50% each of total sample size) and Region (North America versus Rest of World; neither region will enroll more than 60% of the total sample size).

CM is defined as:

- ≥ 15 headache days of which ≥ 8 headache days meet criteria as migraine days during the baseline period based on the electronic diary (eDiary) calculations

EM is defined as:

- < 15 headache days of which at least 4 or more headache days meet criteria as migraine days during the baseline period based on the eDiary calculations

After signing the informed consent form, subjects will enter the screening period. The entire screening period includes a screening period (up to 3 weeks) followed by a 4-week baseline period. At the day 1 visit (the day 1 visit must occur 28 to 35 days after the week -4 baseline period visit date), eligible subjects will be randomized into the 12-week DBTP and will begin to receive double-blind investigational product. At the week 10 visit, subjects will take the last dose of investigational product. At the week 12 visit, subjects will end the DBTP. A safety follow-up period will be conducted 18 weeks after the last dose of investigational product (16 weeks after DBTP). Subjects will use an eDiary every day throughout the baseline period, DBTP, and safety follow-up period to report information about the migraine and non-migraine headaches and acute medication use. Subjects will have in-clinic study visits Q2W after day 1 through the week 12 visit and then Q4W.

The overall study design is described by a study schema in [Section 2.1](#) of the protocol.

3.2 Sample Size

CCI

